4.1.1.2.1. Treatment Group D (INCAGN01876 + Nivolumab + Ipilimumab)

Treatment Group D will treat subjects with INCAGN01876 at the assigned dose level administered IV Q2W in combination with 3 mg/kg of nivolumab administered IV Q2W and 1 mg/kg of ipilimumab administered IV Q6W (see Figure 5). **There will be a waiting period of 48 hours between dose administration of the first subject and second subject of each dosing cohort.** The first 3 evaluable subjects enrolled within a cohort will be observed for 28 days before the next cohort begins enrollment. Dose escalation of INCAGN01876 will proceed as outlined in Table 2 until the MTD or PAD of INCAGN01876 in combination with nivolumab and ipilimumab is determined; however, the dose of INCAGN01876 in the triplet combination will not exceed the lowest MTD of INCAGN01876 established in the applicable doublet combinations. For example, if the MTD of INCAGN01876 in combination with nivolumab is 5 mg/kg and the MTD of INCAGN01876 in combination with ipilimumab is 3 mg/kg, then the dose of INCAGN01876 would not exceed 3 mg/kg.

[figure not shown]
Figure 5: Dosing Figure for Treatment Group D (INCAGN01876 + Nivolumab + Ipilimumab)

4.1.1.2.2. Treatment Group E (INCAGN01876 Sequenced Followed by Concurrent Dosing + Nivolumab + Ipilimumab)

Treatment Group E will treat subjects with INCAGN01876 at the assigned dose level administered IV Q2W for 2 doses followed by INCAGN01876 at the assigned dose level Q2W in combination with 3 mg/kg of nivolumab administered IV Q2W, and 1 mg/kg of ipilimumab administered IV Q6W (see Figure 6). Alternate dose administration schedules may also be explored depending on [REDACTED] safety results. The first 3 evaluable subjects enrolled within a cohort will be observed for 28 days starting after the first dose of nivolumab and ipilimumab has been administered before the next cohort begins enrollment. Dose escalation of INCAGN01876 will proceed as outlined in Table 2 until the MTD or PAD of INCAGN01876 in combination with nivolumab and ipilimumab is determined; however, the dose of INCAGN01876 in the triplet combination will not exceed the lowest MTD of INCAGN01876 established in the applicable doublet combinations. For example, if the MTD of INCAGN01876 in combination with nivolumab is 5 mg/kg and the MTD of INCAGN01876 in combination with ipilimumab is 3 mg/kg, then the dose of INCAGN01876 would not exceed 3 mg/kg.

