4.1.2. Phase 2 – Dose Expansion

Phase 2 of the study will further evaluate the safety, tolerability, efficacy, [REDACTED] and pharmacologic activity of the immune therapy combinations in subjects with advanced or metastatic cervical cancer, gastric cancer (including stomach, esophageal, and GEJ), SCCHN, PD-1 refractory SCCHN, and PD-1 or PD-L1 relapsed melanoma. Additional tumor-specific cohorts may be added, by protocol amendment, based on emerging data. Alternate dose administration schedules and/or fixed doses of INCAGN01876 (comparable to or less than the highest dose levels determined to be safe or pharmacologically active) may also be explored depending on [REDACTED] safety results.

[REDACTED]

The Phase 2 expansion treatment groups and tumor-specific cohorts for each treatment group are outlined in Table 5. A Simon 2-stage design will be used for the cervical cancer, gastric cancer, SCCHN, and PD-1/PD-L1 relapsed melanoma cohorts in each treatment group with a stopping rule to allow for early termination of a particular cohort at the end of Stage 1 if there are insufficient responses observed (Simon 1989). The approximate number of subjects for Stage 1 and Stage 2 for the cervical cancer, gastric cancer, SCCHN, and PD-1/PD-L1 relapsed melanoma cohorts in each treatment group is described in Table 19 and Figure 1. For the PD-1 refractory SCCHN cohort, a Simon 2-stage design with an expansion stage will be used, with stopping rules to allow for early termination if there is an insufficient number of responses observed at the end of Stage 1 or Stage 2. The approximate number of subjects for Stage 1, Stage 2, and the Expansion Stage for the PD-1 refractory SCCHN cohort in Treatment Group F is described in Table 20 and Figure 1. Enrollment in Phase 2 will begin when the MTD or PAD of INCAGN01876 for a given treatment group in Phase 1 has been determined.

Table 5: Phase 2 Expansion Treatment Groups

Doublet Expansion Treatment Groups				
Treatment Group C2	INCAGN01876 Concurrent Dosing	Ipilimumab		Tumor Cohorts
	RP2D of INCAGN01876 Q2W	1 mg/kg Q6W		Cohort 1 – PD-1/PD-L1 relapsed melanoma ██████████
Treatment Group F	INCAGN01876 Concurrent Dosing	Nivolumab		Tumor Cohorts
	RP2D of INCAGN01876 Q2W	240 mg Q2W		Cohort 1 – Cervical Cohort 2 – Gastric Cohort 3 – SCCHN Cohort 4- PD-1/PD-L1 relapsed melanoma ██████████ Cohort 6 – PD-1 refractory SCCHN
Treatment Group H	INCAGN01876 Sequenced Followed by Concurrent Dosing	Nivolumab		Tumor Cohorts

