	RP2D of INCAGN01876 run-in Q2W for 2 doses followed by INCAGN01876 Q2W	240 mg Q2W starting at Cycle 3 in combination with INCAGN01876 Q2W		Cohort 1 –Cervical Cohort 2 – Gastric Cohort 3 – SCCHN ██████████
Triplet Expansion Treatment Groups				
Treatment Group J	INCAGN01876 Concurrent Dosing	Nivolumab	Ipilimumab	Tumor Cohorts
	RP2D of INCAGN01876 Q2W	3 mg/kg Q2W	1 mg/kg Q6W	Cohort 1 – Cervical Cohort 2 – Gastric Cohort 3 – SCCHN ██████████
Treatment Group L	INCAGN01876 Sequenced Followed by Concurrent Dosing	Nivolumab	Ipilimumab	Tumor Cohorts
	RP2D of INCAGN01876 run-in Q2W for 2 doses followed by INCAGN01876 Q2W	3 mg/kg Q2W starting at Cycle 3	1 mg/kg Q6W starting at Cycle 3	Cohort 1 – Cervical Cohort 2 – Gastric Cohort 3 – SCCHN ██████████

In Phase 2 of the study, toxicities will continue to be monitored. If the cumulative incidence of Grade 3 or higher INCAGN01876-related AEs occurs in > 40% of subjects in a particular treatment group after 6 subjects have been enrolled, then further enrollment in that treatment group will be interrupted until the sponsor, investigators, and regulatory authorities (if applicable) determine the appropriate course of action (eg, lower the dose of INCAGN01876, change dose frequency, etc). If a treatment group is discontinued due to toxicity, it may be re-initiated at a previously tested lower dose level and/or alternate dosing schedule. All AEs, regardless of the time of occurrence on study, may be considered for DLT determination purposes.

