#### **4.1.6. Cycle Length and Duration**

Cycle 1 Day 1 is the day that the first dose of INCAGN01876, nivolumab, or ipilimumab is administered. One treatment cycle consists of 14 days. The first cycle of therapy is defined as the period beginning with the first dose of INCAGN01876, nivolumab, or ipilimumab and ending the earlier of the following 1) 14 calendar days (inclusive later) or 2) permanent discontinuation of 1 or more of the following: INCAGN01876, nivolumab, and ipilimumab. Subsequent cycles have Day 1 as the corresponding visit date associated with the corresponding cycle. Note that dosing of ipilimumab is once every 6 weeks.

In Phase 2, subjects in Treatment Groups F and H will be administered INCAGN01876 at the RP2D determined by Treatment Group A along with nivolumab and subjects in Treatment Group G will be administered INCAGN01876 at the RP2D determined by Treatment Group B along with nivolumab. Subjects in Treatment Groups J and L will be administered INCAGN01876 at the RP2D determined by Treatment Group D along with nivolumab and ipilimumab and subjects in Treatment Groups K will be administered INCAGN01876 at the RP2D determined by Treatment Group E along with nivolumab and ipilimumab.

Subjects will continue to receive INCAGN01876, nivolumab, and ipilimumab as defined in the protocol as long as the subject is deriving benefit and has not met any of the Protocol-defined conditions for treatment withdrawal.

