### 5.2. Treatment Groups

This is a Phase 1/2, open-label, nonrandomized, multicenter, dose-escalation study. In Phase 1, because the starting dose of INCAGN01876 is 1.0 mg/kg in Cohort 3, up to 4 doses of INCAGN01876 will be tested. Data will be summarized by treatment group and by dose level.

Dose escalation of the triplet immune therapy combinations will begin enrolling once all of the applicable doublet combinations have cleared 3 INCAGN01876 dose levels (see [Table 1](#)) or the MTD or PAD of INCAGN01876 has been determined (whichever occurs first). The starting dose of INCAGN01876 will be 2 dose levels below the last dose cohort deemed safe in the doublet combination. The triplet immune therapy combinations will be explored in parallel as outlined in [Figure 1](#).

- Treatment Group A:
  - INCAGN01876 1.0 mg/kg + nivolumab 240 mg
  - INCAGN01876 3.0 mg/kg + nivolumab 240 mg
  - INCAGN01876 5.0 mg/kg + nivolumab 240 mg
  - INCAGN01876 10.0 mg/kg + nivolumab 240 mg
- Treatment Group B
  - 1.0 mg/kg run-in with INCAGN01876 × 2 doses followed by nivolumab 240 mg
  - 3.0 mg/kg run-in with INCAGN01876 × 2 doses followed by nivolumab 240 mg
  - 5.0 mg/kg run-in with INCAGN01876 × 2 doses followed by nivolumab 240 mg
  - 10.0 mg/kg run-in with INCAGN01876 × 2 doses followed by nivolumab 240 mg
- Treatment Group C
  - INCAGN01876 1.0 mg/kg + ipilimumab 1 mg/kg
  - INCAGN01876 3.0 mg/kg + ipilimumab 1 mg/kg
  - INCAGN01876 5.0 mg/kg + ipilimumab 1 mg/kg
  - INCAGN01876 10.0 mg/kg + ipilimumab 1 mg/kg

- Treatment Group D
  - INCAGN01876 1.0 mg/kg + nivolumab 3 mg/kg + ipilimumab 1 mg/kg
  - INCAGN01876 3.0 mg/kg + nivolumab 3 mg/kg + ipilimumab 1 mg/kg
  - INCAGN01876 5.0 mg/kg + nivolumab 3 mg/kg + ipilimumab 1 mg/kg
  - INCAGN01876 10.0 mg/kg + nivolumab 3 mg/kg + ipilimumab 1 mg/kg
- Treatment Group E
  - 1.0 mg/kg run-in with INCAGN01876 × 2 doses followed by nivolumab 3 mg/kg + ipilimumab 1 mg/kg
  - 3.0 mg/kg run-in with INCAGN01876 × 2 doses followed by nivolumab 3 mg/kg + ipilimumab 1 mg/kg
  - 5.0 mg/kg run-in with INCAGN01876 × 2 doses followed by nivolumab 3 mg/kg + ipilimumab 1 mg/kg
  - 10.0 mg/kg run-in with INCAGN01876 × 2 doses followed by nivolumab 3 mg/kg + ipilimumab 1 mg/kg

In Phase 2, endometrial, gastric, SCCHN subjects and a separate biopsy cohort will be enrolled in each treatment group. Data will be summarized by treatment group and tumor type-specific cohort.

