- Treatment Group F: RP2D from Treatment Group A INCAGN01876 + nivolumab 240 mg
  - Cohort 1: Endometrial
  - Cohort 2: Gastric
  - Cohort 3: SCCHN
  - Cohort 4: Biopsy
- Treatment Group G: RP2D from Treatment Group B INCAGN01876 run-in Q2W × 2 doses followed by nivolumab 240 mg Q2W
  - Cohort 1: Endometrial
  - Cohort 2: Gastric
  - Cohort 3: SCCHN
  - Cohort 4: Biopsy
- Treatment Group H: RP2D from Treatment Group A INCAGN01876 run-in Q2W × 2 doses followed by nivolumab 240 mg Q2W + INCAGN01876 Q2W
  - Cohort 1: Endometrial
  - Cohort 2: Gastric

- Cohort 3: SCCHN
- Cohort 4: Biopsy
- Treatment Group J: RP2D from Treatment Group D INCAGN01876 + nivolumab 3 mg/kg Q2W + ipilimumab 1 mg/kg Q6W
  - Cohort 1: Endometrial
  - Cohort 2: Gastric
  - Cohort 3: SCCHN
  - Cohort 4: Biopsy
- Treatment Group K: RP2D from Treatment Group E INCAGN01876 run-in Q2W × 2 doses followed by nivolumab 3 mg/kg Q2W + ipilimumab 1 mg/kg Q6W
  - Cohort 1: Endometrial
  - Cohort 2: Gastric
  - Cohort 3: SCCHN
  - Cohort 4: Biopsy
- Treatment Group L: RP2D from Treatment Group D INCAGN01876 run-in Q2W × 2 doses followed by INCAGN01876 Q2W + nivolumab 3 mg/kg Q2W + ipilimumab 1 mg/kg Q6W
  - Cohort 1: Endometrial
  - Cohort 2: Gastric
  - Cohort 3: SCCHN
  - Cohort 4: Biopsy

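### The SAP still takes Group L's dose from Group D and uses Group E's only for the removed Group K, although Group E now tests Group L's exact schedule

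*SAP*

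**What the plan says.** **SAP, source of the triplet doses.** SAP 4.1.6 ties two of the triplet groups to Group D: "Subjects in Treatment Groups J and L will be administered INCAGN01876 at the RP2D determined by Treatment Group D along with nivolumab and ipilimumab". The third triplet group is handled separately in the same paragraph, where the rule is that "subjects in Treatment Groups K will be administered INCAGN01876 at the RP2D determined by Treatment Group E". The treatment-group list in SAP 5.2 repeats both rules. Its entry for L begins "Treatment Group L: RP2D from Treatment Group D INCAGN01876 run-in Q2W", and its entry for K begins "Treatment Group K: RP2D from Treatment Group E INCAGN01876 run-in Q2W".

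**SAP, Group E.** SAP 5.2 describes Group E's first dose level as "1.0 mg/kg run-in with INCAGN01876 × 2 doses followed by nivolumab 3 mg/kg + ipilimumab 1 mg/kg", with no INCAGN01876 after the run-in. That is Group K's schedule.

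**Current protocol, Group E.** Protocol 4.1.1.2.2 has two run-in "doses followed by INCAGN01876 at the assigned dose level Q2W in combination with" nivolumab 3 mg/kg Q2W and ipilimumab 1 mg/kg Q6W.

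**Current protocol, Phase 2.** Table 5 lists Groups C2, F, H, J and L; there is no Group K. Group L receives "RP2D of INCAGN01876 run-in Q2W for 2 doses followed by INCAGN01876 Q2W", with nivolumab 3 mg/kg Q2W and ipilimumab 1 mg/kg Q6W from Cycle 3.

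**Opening Phase 2.** Protocol 4.1.2: "Enrollment in Phase 2 will begin when the MTD or PAD of INCAGN01876 for a given treatment group in Phase 1 has been determined". SAP 3.2 carries the same sentence.

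**Versions.** SAP 2.1 bases the SAP on Amendment 2 (22 AUG 2017) and keeps it in force for later amendments unless superseded. SAP Table 14 lists only the original, dated 05 DEC 2017. Amendment 3 is dated 18 DEC 2017.

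**The concern.** Under Amendment 2 the mapping made sense. Group E tested the run-in-only schedule and so set the dose for K. No Phase 1 group tested L's schedule, so L borrowed the dose from the concurrent triplet, Group D. Group E has since been changed to L's schedule and K has been removed, but the SAP mapping has not moved.

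Applied to the current groups, the SAP sends D's RP2D to J and L, and sends E's RP2D to a group that is no longer there. Two things follow. The escalation run on L's own schedule sets no Phase 2 dose. And if E's MTD came out below D's, the SAP would still give L the dose chosen from D. At stake are the justification for L's dose and an accurate account of where it came from.

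The line could survive a routine update. Deleting the removed groups would not touch it, because D and L both still exist.

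**Working it through.** **1. Mapping check.** This part needs no arithmetic; the texts are set side by side.

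| Item | SAP 4.1.6 and 5.2 | Current protocol |
|---|---|---|
| Group D | Concurrent triplet | Concurrent triplet (4.1.1.2.1) |
| Group E | Run-in × 2, then nivolumab + ipilimumab | Run-in × 2, then INCAGN01876 + nivolumab + ipilimumab (4.1.1.2.2) |
| Group K | Run-in only; dose from E | Not in Table 5 |
| Group L | Run-in, then concurrent; dose from D | Run-in, then concurrent (Table 5); source group not named in visible text |
| DLT window | – | D from Cycle 1 Day 1; E and L from Cycle 3 Day 1 (5.4.2) |

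Group E matches L on the run-in, the later INCAGN01876 dosing, the nivolumab and ipilimumab doses and start, and the DLT window. Group D matches on the drugs only.

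**2. Contrast with Group H.** SAP 4.1.6 doses H (run-in, then concurrent doublet) from concurrent Group A. That can stand. Group B still gives INCAGN01876 only in Cycles 1 and 2 (Protocol 5.2.1.1), so no Phase 1 group tests H's schedule. For L, one now does.

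**3. Size of Group L.** From Protocol Table 19, triplet rows:
- Cervical 48 + gastric 50 + SCCHN 50 = 148 if all three cohorts complete.
- Visible Phase 2 stages (Protocol 4.3.1): 264 + 455 + 20 = 739.
- Share: 148 / 739 = 20.0%.
- The overall maximum less Phase 1 is 1039 − 270 = 769, so 769 − 739 = 30 further subjects fall in a redacted line. They are left out of both numerator and denominator.

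**4. Effect on L's DLT rate.** First, the plan's own figures. With true DLT rate p, q0 = (1−p)³ and q1 = 3p(1−p)²:

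P(escalate) = q0 + q1·q0 + q1²·q0.

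At p = 20%: q0 = 0.512 and q1 = 0.384, so 0.512 × (1 + 0.384 + 0.1475) = 78.4%. At 30% the formula gives 56.1%. Both agree with Protocol Table 18.

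Now run D and E as two independent escalations over the four levels in SAP Table 1, with the *same* true rates. The rates are assumptions, since the documents give none.

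| True DLT rates, four levels | E ends below D | Same level | E ends above D |
|---|---|---|---|
| 2% at all | 0.6% | 98.8% | 0.6% |
| 5% at all | 4.2% | 91.7% | 4.2% |
| 5/10/15/20% | 26.7% | 46.6% | 26.7% |
| 10/20/30/40% | 37.7% | 24.6% | 37.7% |

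E can land below D by chance, and it lands above D equally often. With equal rates the selected level has the same distribution in both groups, so L's expected true DLT rate is the same from either source: the difference is 0.

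The source matters in expectation only if the schedules differ in toxicity. As an illustration, suppose L's schedule had 1.5 times D's rates at every level, an assumption with no support in the documents. Given at least one tolerated level, L's mean true DLT rate dosed from D versus from E would be:
- 7.5% vs 7.5% (D at 5% throughout);
- 25.8% vs 21.6% (D at 5/10/15/20%);
- 35.7% vs 25.8% (D at 10/20/30/40%).

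The difference is thus 0 to 9.9 percentage points across these cases. Dose selection on PAD and the lowest-doublet-MTD cap are not modelled.

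**The case against.** The strongest reply is that this is version lag in a document that does not set doses. The SAP was written to Amendment 2, and its purpose is analysis detail (SAP 1). Dosing follows the protocol, whose text can be read as tying L to E: Phase 2 opens on the MTD or PAD for the given treatment group (4.1.2), and Stage 1 subjects are treated at the MTD or PAD and schedule for the corresponding cohort (9.2.2). Figure 1 is not shown and may name the source. Safeguards also apply: L has its own 28-day DLT window (5.4.2), enrollment in a group is interrupted above 40% Grade 3 or higher related AEs after 6 subjects (4.1.2), and the Phase 1 triplet doses are capped at the lowest doublet MTD (4.1.1.2.1 and 4.1.1.2.2). Enrollment is complete (Appendix C, Amendment 5).

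Much of this stands, and it limits the consequence. It does not remove the mismatch. SAP 2.1 keeps the SAP in force for later amendments and no later version is listed. The SAP repeats the protocol sentences on opening Phase 2 and on schedule (SAP 3.2 and 3.4.2), so its rule for L now sits badly with its own text.

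Three stronger readings are tempting, and the documents do not support them:
- **L was overdosed.** Nothing shows E's MTD below D's, a more toxic run-in schedule, or even that L enrolled anyone.
- **Every display by treatment group misstates L's dose.** No table, figure or listing title in SAP Appendix A refers to a source group, and INCAGN01876 exposure is computed from the dose actually given (SAP 6.4.1).
- **An escalation with no Phase 2 user is itself a defect.** Group B has none either, since G was removed. The issue with E is that a Phase 2 group on its schedule exists and the SAP points that group elsewhere.

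**Conclusion.** The point holds as a minor inconsistency. SAP 4.1.6 and 5.2 are wrong as written for the current design: they tie L to a Phase 1 group on a different schedule and leave the group on L's own schedule without a role in Phase 2 dose selection. Whether the line contradicts the protocol or is the only explicit rule cannot be settled from the visible text.

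The reach is at most 148 of 739 subjects in the visible Phase 2 stages (20%), if all three L cohorts complete. The expected effect on L's true DLT rate is zero under equal toxicity in D and E; any other figure rests on an assumed difference between schedules. Because enrollment is complete, what can still be put right is the written rule, a check of L's dose, and the report.

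**What to change.** - **SAP 4.1.6 and 5.2:** assign Group L the RP2D from Group E, not above E's MTD. Delete the Group K mapping. Update the Group E description in SAP 5.2 to the current schedule. Group H's source (Group A) can stay.
- **Protocol Table S4 and Table 5:** name Group E as L's source, unless Figure 1 already does.
- **Retrospective check:** compare the INCAGN01876 dose that any L subjects received with E's MTD.
- **Clinical study report:** state L's actual dose and which Phase 1 group it came from. If J and L had different doses, say that any comparison of J with L mixes dose with schedule, and that any pooling containing both, such as the within-tumor-type pooling (Protocol 9.6.2, SAP Table 12), mixes doses.

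The cost is a few lines of wording and one data check, with no extra patients. None of it can change doses already given.

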## **4.2. Variable Definitions**

### **4.2.1. Variables to Be Derived Only If Not Provided on Case Report Form**

The following variables will only be calculated if not reported on the CRF:

- Subject age will be calculated as the integer part of the number of years from date of birth to the date of signing the informed consent form (ICF), using the following formula:

$$\text{Age} = \text{integer part of } (\text{date of informed consent} - \text{date of birth} + 1) / 365.25$$

### **4.2.2. Prior and Concomitant Medication**

Prior medication is defined as any nonstudy medication started before the first dose of INCAGN01876, nivolumab, or ipilimumab.

Concomitant medication is defined as any nonstudy medication that is started accordingly:

- Before the date of first administration of INCAGN01876, nivolumab, or ipilimumab and is ongoing throughout the study or ends on/after the date of first study treatment administration.
- On/after the date of first administration of INCAGN01876, nivolumab, or ipilimumab and is ongoing or ends during the course of study treatment.

A prior medication could also be classified as "both prior and concomitant medication" if the end date is on or after first dose of INCAGN01876, nivolumab, or ipilimumab. In the listing, it will be indicated whether a medication is prior-only, concomitant-only, or both prior and concomitant medication.

For the purposes of analysis, all medications will be considered concomitant medications unless the medications can unequivocally be defined as not concomitant.

## 5. STATISTICAL METHODOLOGY

### 5.1. General Methodology

Unless otherwise noted, SAS® software (SAS Institute Inc, Cary, NC; Version 9 or later) will be used for the generation of all tables, graphs, and statistical analyses. Descriptive summaries for continuous variables will include, but not be limited to, the number of observations, mean, standard deviation, median, minimum, and maximum. Descriptive summaries for categorical variables will include the number and percentage of subjects in each category.

Interim analyses are planned for this study as defined in Section 9.

### 5.2. Treatment Groups

This is a Phase 1/2, open-label, nonrandomized, multicenter, dose-escalation study. In Phase 1, because the starting dose of INCAGN01876 is 1.0 mg/kg in Cohort 3, up to 4 doses of INCAGN01876 will be tested. Data will be summarized by treatment group and by dose level.

Dose escalation of the triplet immune therapy combinations will begin enrolling once all of the applicable doublet combinations have cleared 3 INCAGN01876 dose levels (see [Table 1](#)) or the MTD or PAD of INCAGN01876 has been determined (whichever occurs first). The starting dose of INCAGN01876 will be 2 dose levels below the last dose cohort deemed safe in the doublet combination. The triplet immune therapy combinations will be explored in parallel as outlined in [Figure 1](#).

- Treatment Group A:
  - INCAGN01876 1.0 mg/kg + nivolumab 240 mg
  - INCAGN01876 3.0 mg/kg + nivolumab 240 mg
  - INCAGN01876 5.0 mg/kg + nivolumab 240 mg
  - INCAGN01876 10.0 mg/kg + nivolumab 240 mg
- Treatment Group B
  - 1.0 mg/kg run-in with INCAGN01876 × 2 doses followed by nivolumab 240 mg
  - 3.0 mg/kg run-in with INCAGN01876 × 2 doses followed by nivolumab 240 mg
  - 5.0 mg/kg run-in with INCAGN01876 × 2 doses followed by nivolumab 240 mg
  - 10.0 mg/kg run-in with INCAGN01876 × 2 doses followed by nivolumab 240 mg
- Treatment Group C
  - INCAGN01876 1.0 mg/kg + ipilimumab 1 mg/kg
  - INCAGN01876 3.0 mg/kg + ipilimumab 1 mg/kg
  - INCAGN01876 5.0 mg/kg + ipilimumab 1 mg/kg
  - INCAGN01876 10.0 mg/kg + ipilimumab 1 mg/kg

- Treatment Group D
  - INCAGN01876 1.0 mg/kg + nivolumab 3 mg/kg + ipilimumab 1 mg/kg
  - INCAGN01876 3.0 mg/kg + nivolumab 3 mg/kg + ipilimumab 1 mg/kg
  - INCAGN01876 5.0 mg/kg + nivolumab 3 mg/kg + ipilimumab 1 mg/kg
  - INCAGN01876 10.0 mg/kg + nivolumab 3 mg/kg + ipilimumab 1 mg/kg
- Treatment Group E
  - 1.0 mg/kg run-in with INCAGN01876 × 2 doses followed by nivolumab 3 mg/kg + ipilimumab 1 mg/kg
  - 3.0 mg/kg run-in with INCAGN01876 × 2 doses followed by nivolumab 3 mg/kg + ipilimumab 1 mg/kg
  - 5.0 mg/kg run-in with INCAGN01876 × 2 doses followed by nivolumab 3 mg/kg + ipilimumab 1 mg/kg
  - 10.0 mg/kg run-in with INCAGN01876 × 2 doses followed by nivolumab 3 mg/kg + ipilimumab 1 mg/kg

In Phase 2, endometrial, gastric, SCCHN subjects and a separate biopsy cohort will be enrolled in each treatment group. Data will be summarized by treatment group and tumor type-specific cohort.

- Treatment Group F: RP2D from Treatment Group A INCAGN01876 + nivolumab 240 mg
  - Cohort 1: Endometrial
  - Cohort 2: Gastric
  - Cohort 3: SCCHN
  - Cohort 4: Biopsy
- Treatment Group G: RP2D from Treatment Group B INCAGN01876 run-in Q2W × 2 doses followed by nivolumab 240 mg Q2W
  - Cohort 1: Endometrial
  - Cohort 2: Gastric
  - Cohort 3: SCCHN
  - Cohort 4: Biopsy
- Treatment Group H: RP2D from Treatment Group A INCAGN01876 run-in Q2W × 2 doses followed by nivolumab 240 mg Q2W + INCAGN01876 Q2W
  - Cohort 1: Endometrial
  - Cohort 2: Gastric

- Cohort 3: SCCHN
- Cohort 4: Biopsy
- Treatment Group J: RP2D from Treatment Group D INCAGN01876 + nivolumab 3 mg/kg Q2W + ipilimumab 1 mg/kg Q6W
  - Cohort 1: Endometrial
  - Cohort 2: Gastric
  - Cohort 3: SCCHN
  - Cohort 4: Biopsy
- Treatment Group K: RP2D from Treatment Group E INCAGN01876 run-in Q2W × 2 doses followed by nivolumab 3 mg/kg Q2W + ipilimumab 1 mg/kg Q6W
  - Cohort 1: Endometrial
  - Cohort 2: Gastric
  - Cohort 3: SCCHN
  - Cohort 4: Biopsy
- Treatment Group L: RP2D from Treatment Group D INCAGN01876 run-in Q2W × 2 doses followed by INCAGN01876 Q2W + nivolumab 3 mg/kg Q2W + ipilimumab 1 mg/kg Q6W
  - Cohort 1: Endometrial
  - Cohort 2: Gastric
  - Cohort 3: SCCHN
  - Cohort 4: Biopsy

